¹⁵Endogenous subgroups are groups of participants that are defined by an outcome measure. The expected balance in observed and unobserved characteristics between treatment and control participants that results from random assignment cannot be guaranteed in such subgroups and thus effect estimates may be subject to bias. Tests of baseline balance will be conducted; if we have reason to believe there is imbalance between treatment and comparison groups for this outcome, we will reduce this to an exploratory research question.

It should be noted that this measure will only be constructed for individuals who select either *None*, *Oral contraceptives*, *The patch*, *The shot/injection*, or *The ring* to the question “Which of the following birth control methods are you currently using?”. If an individual selects *The implant* or *IUD* to this question, the individual will be excluded from analysis of this measure. As such, the subgroup of participants in which we conduct this analysis will be considered an endogenous subgroup (i.e. not inclusive of our full analytic sample) because it is constructed based on a participant’s response to an outcome measure.¹⁶

Plan A will be considered to have a positive impact on use of other effective contraceptive methods if, as compared to participants who are assigned to the control group, a larger proportion of participants who are offered *Plan A* report using other effective contraceptive methods at the three-month follow-up and the difference between groups is statically significant.

- b. **Analytic sample:** In Central California, eight clinics have been recruited to participate in the study. As explained in the *Study Design* section, clinic-based study coordinators review administrative/clinic data for patients with appointments at the study clinics to identify potentially eligible participants.

Potential participants are eligible if they: 1) are female; 2) are between the ages of 18 and 19 years of age; 3) are Hispanic and/or Latina; 4) are not knowingly pregnant or trying to get pregnant; 5) consent/assent to participate; 6) did not enroll in the SpeakOut study between November 2016 to October 2018¹⁷; and 7) are deemed appropriate for the study with regards to physical and mental health by a clinician, clinic staff, or the study coordinator.

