After eligibility is determined, participants are randomized into the treatment (*Plan A*) or control (*The Toxic Life Cycle of a Cigarette*) condition according to procedures detailed in subsection 3b. The act of randomization into either the treatment or control arm constitutes the offer to participate in the intervention and is the point at which the individual becomes a participant in the study. The analytic sample is defined as all participants who were randomized into either the treatment or control conditions and who have reported sufficient outcome and covariate data.¹⁸ Missing data procedures are outlined in subsection 4cv below.

- c. **Data cleaning:** Prior to analysis, PRG staff will systematically screen or review the analytic variables (baseline and outcome) to identify invalid, inconsistent, outlying, missing, and unreliable data.¹⁹ New variables are created in which data that are deemed unusable (i.e., invalid

¹⁶ See footnote 15.

¹⁷ See footnote 4.

¹⁸ As outlined in subsection 4cv, our benchmark approach is to impute baseline/covariate data. As such, sufficient baseline/covariate data means all cases where data are not unit missing. We do not anticipate that we will have different analytic samples for our outcomes of interest; data are expected to be missing entirely for any given respondent at any observation point or not. If for whatever reason analytic samples are different for different outcomes, we will assess baseline equivalence separately for each analytic sample.

¹⁹ We propose to document the prevalence of inconsistent and missing data in a descriptives table presented as an appendix in our final impact report. Along with our presentation of sensitivity analyses, we will present tables that present the prevalence of unit and item missing (which result from nonresponse) as well as inconsistent, unreliable, and invalid data for both treatment and control samples. Regarding inconsistencies specifically, for each sexual behavior variable included in our model specifications (which could therefore influence the constitution of the analytic sample) we will include the following: sample size (the number of observations prior to recoding of inconsistencies) and the number of observations that are inconsistent over-time. If paper questionnaires lead to internally inconsistent data, we will also report on this.

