 4. Determine if any individuals who are in the randomized sample have no data at all (i.e., unit missing) at baseline and at the three-month follow-up time point. If this is the case, our proposed benchmark approach is to use case deletion, as we feel it is the most straightforward and prudent approach for missing follow-up data recommended in Puma et al. (2009). These cases will be deleted from the analytic sample and attrition statistics will be reported.
 5. Determine if any individuals who are in the randomized sample (for each outcome) are missing baseline covariates or the baseline measure of the outcome variable. If this is the case, our proposed benchmark approach is to use dummy variable adjustment procedures, as we feel it is the most straightforward and prudent approach for missing baseline/covariate data recommended in Puma et al. (2009).
 6. Conduct sensitivity analyses by estimating results with missing baseline data excluded from the analysis (i.e., use case-wise deletion for all cases with missing baseline and outcome data). In an appendix, we will report our benchmark results next to the sensitivity analysis results to verify findings.
- d. **Assessment of baseline equivalence:** Baseline equivalence will be reported for all baseline measures of each outcome variable as well as relevant demographic and sexual behavioral measures. We first list and describe the measures we will use to examine the equivalence of our treatment and control group at baseline. After we identify the measures, we provide details on the diagnostic methods that we will use to assess any baseline difference that may exist between the treatment and control groups in the measures outlined below.

Demographic and Sexual Behavior Measures

Baseline equivalence will be assessed for four demographic variables and one baseline measure of sexual behavior (identified below). Each of the variables are constructed from participant self-responses to questions in either the *Eligibility Screening Form* or VHS baseline *Participant Questionnaire*. For the race variables, categorical responses to a single question are used to create multiple dichotomous variables. The sexual behavioral variable is constructed from participants' responses to three questions in the baseline *Participant Questionnaire*. We provide details on

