To establish baseline equivalence, we propose to generate model-based point estimates of the difference between the treatment and control groups for the identified baseline equivalence variables. We will report the adjusted means and p-values of the differences in the baseline variable of interest for the treatment and control groups. We will then compute the pooled standard deviation of these variables. Finally, we will produce a standardized difference of means by dividing the first term by the second.³⁵

step 1. First, we generate a model-based estimate of the difference between treatment and comparison groups on the pre-intervention measures identified above. Separate models will be run for each of the variables. The empirical model will be estimated with OLS (using Stata). If the measure is dichotomous we propose to use a linear probability model to estimate the predicted probability of group membership. The model is a reduced-form variation of the model that we use to estimate program impact (as detailed in the *Model specification and covariates* section, below).³⁶

$$Y_{baseline} = \beta_0 + \beta_1 T + \sum (\beta_p X_p) + \varepsilon$$

where:

$Y_{baseline}$ – is the baseline measure of the variable that we use to establish baseline equivalency (identified in Appendix A – Table 2). This variable is included as a covariate in the analytic model (see Table 2 for details on variable coding). Separate models will be estimated for each baseline equivalency measure specified above.

T – A dummy treatment indicator variable whose value equals 1 if the participant is randomized into the treatment group and zero otherwise.

X – Region (blocking variable) – An n-1 vector of region indicator dummy variables that are coded one if the intervention was delivered at region n and coded zero otherwise.

β_0 – The intercept term, which represents the adjusted mean value of the baseline equivalency measure for participants in the control sample, with all other variables in the model held constant at zero.

β_1 – This represents the adjusted (but not standardized) mean difference in the baseline equivalency variable between treatment and control participants.

ε – The residual or random variation that remains for each observation after the structural components of the model are estimated. It is the difference between the observed and the predicted values at the individual level.

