step 2. Report the adjusted means and p-values of the differences in the baseline variable of interest for the treatment and control groups.

step 3. If the pre-intervention measure is continuous, we propose to use the following formula to calculate the pooled within-group standard deviation of the outcome measure:

$$S_p = \sqrt{\frac{(n_t - 1)S_t^2 + (n_c - 1)S_c^2}{(n_t + n_c - 2)}}$$

³⁵ Note that we will produce diagnostic estimates of baseline equivalence on the exact same samples of observations that we will use in our primary, secondary, and exploratory analyses. In other words, we will apply the missing data approach outlined in subsection 4cv prior to producing estimates of baseline equivalency on the pre-intervention measures. To validate this benchmark approach, we will also produce a sensitivity analysis that produces estimates of baseline equivalency without imputations (i.e., with all missing data). Benchmark and sensitivity estimates of baseline equivalency will be presented beside each other in an appendix.

³⁶ It is a reduced-form because individual-level, demographic covariates are omitted. It is a variation because the dependent variable is the baseline equivalence variable, not the outcome measure.

where: n_t and n_c are the sample sizes, and S_t and S_c are the participant-level standard deviations for the pre-intervention measures for the analytic treatment and comparison groups, respectively. We will produce separate calculations of the pooled standardized deviation for each variable used to establish baseline equivalence (as noted above).

step 4. Produce the standardized difference of means. If the pre-intervention measure is continuous, we will use Hedges' g as the formula to compute the standardized difference of means for the treatment and comparison groups:

$$g = \frac{\beta_1}{S_p}$$

Where: β_1 is the adjusted mean difference in the variable selected to establish baseline equivalence for the treatment and comparison groups (calculated in Step 1), and S_p is the pooled standard deviation (produced in Step 2).

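### The benchmark baseline-balance estimates use baseline values filled by dummy-variable adjustment, a device that does not suit a dependent variable; the valid observed-value version is planned only as a sensitivity analysis

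*SAP*

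**What the plan says.** Section 4d (Balance Assessment Methods, step 1) regresses each baseline measure on treatment and region. The left-hand side "is the baseline measure of the variable that we use to establish baseline equivalency", and "Separate models will be estimated for each baseline equivalency measure specified above". Footnote 36 explains the short right-hand side: "It is a reduced-form because individual-level, demographic covariates are omitted". Steps 2 to 4 turn the result into adjusted means, p-values, a pooled SD and a standardised difference (Hedges' g, or the Cox index for dichotomous measures).

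Footnote 35 fixes the order of work for the benchmark: "we will apply the missing data approach outlined in subsection 4cv prior to producing estimates of baseline equivalency on the pre-intervention measures". It then adds a sensitivity version without imputation and puts both sets side by side in an appendix.

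Section 4c.v, step 5, says what happens to a missing baseline value: "our proposed benchmark approach is to use dummy variable adjustment procedures". Footnote 18 (section 4b) describes the same thing as imputation ("our benchmark approach is to impute baseline/covariate data") and defines who is kept: "sufficient baseline/covariate data means all cases where data are not unit missing". So item-missing values are filled and unit-missing cases are not. The constant is not stated.

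One decision depends on balance. Footnote 15 (section 4a, dual methods) says: "Tests of baseline balance will be conducted; if we have reason to believe there is imbalance", the question becomes exploratory. Footnote 16 refers the other-effective-methods outcome to the same note.

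**The concern.** Dummy-variable adjustment keeps a case in a regression when one of its covariates is missing. The constant is harmless there because the flag beside it absorbs its effect. The argument fails when the variable moves to the left-hand side. The constant is then simply an outcome value, and the regression, the SD and the proportions treat it as reported by the participant.

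Footnote 35 has a sound aim, which is to check balance in the people who are analysed. That needs the same participants, not filled values. At stake is the plan's check that loss and exclusion have not disturbed the randomised comparison, and possibly the demotion of two secondary outcomes. The impact estimates are not affected.

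**Working it through.** The plan gives no figure to reproduce, so the effect is derived from its own formulas.

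**Inputs from the SAP.** Balance model with treatment and region only; g = beta-1 / pooled SD; Cox index = [logit(p_t) - logit(p_c)] / 1.65; target sample 1,770, so 885 per arm at 1:1.

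**Assumptions, not in the SAP.** Continuous measure with mean 17 (treatment) v 15 (control) and SD 20, so true g = 2/20 = 0.100; dichotomous measure 25% v 20%, true Cox index 0.174; fill constant c equal to the grand mean, or 0; missing share m from 0 to 20%; values missing at random within arm. Region is left out for simplicity.

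**Formulas.** After filling, without a flag:
- arm mean = (1-m)·mu + m·c
- arm variance = (1-m)·SD² + m(1-m)(mu-c)²

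**Equal missingness, grand-mean fill (c = 16).** The difference shrinks by (1-m) and the SD by about sqrt(1-m), so g shrinks by about sqrt(1-m). At m = 10%: difference 1.8; variance 0.9 × 400 + 0.09 × 1 = 360.09; SD 18.976; g = 0.095.

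| m per arm | g | Cox index |
|---|---|---|
| 0 | 0.100 | 0.174 |
| 2% | 0.099 | 0.171 |
| 5% | 0.097 | 0.166 |
| 10% | 0.095 | 0.157 |
| 20% | 0.089 | 0.139 |

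The shift is towards apparent balance and is small. At 10% missing the p-value is 0.0460 with filling and 0.0460 on observed values.

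**Unequal missingness, zero fill.**
- Treatment 10%, control 5%: means 0.90 × 17 = 15.30 and 0.95 × 15 = 14.25; difference 1.05; pooled SD 19.707; g = 0.053 instead of 0.100.
- Treatment 5%, control 10%: means 16.15 and 13.50; difference 2.65; pooled SD 19.672; g = 0.135.
- Arms truly equal at 15, treatment 10%, control 5%: difference 13.50 - 14.25 = -0.75; pooled SD 19.633; g = -0.038, an imbalance that is not there.
- Dichotomous and truly balanced, 3% v 8% missing: at 60% prevalence the filled proportions are 0.582 and 0.552, Cox index 0.074; at 70% they are 0.679 and 0.644, Cox index 0.095.

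**Would a flag in the balance model repair it?** Not fully. Among flagged cases the arm difference is zero by construction, and that zero is averaged in. With 10% v 5% missing, the weight on the observed difference is [0.90 × 0.95/1.85] / [0.90 × 0.95/1.85 + 0.10 × 0.05/0.15] = 0.4622/0.4955 = 0.933. A simulation with 400,000 records agrees: 1.04 without a flag (zero fill), 1.85 with a flag, 1.99 on observed values (true value 2.00).

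**Which variables can be filled.** Age and race/ethnicity come from the screening form and determine eligibility, so they should rarely be missing. Education, ever had sex and the behavioural measures come from the questionnaire. Section 4c.iv also sets baseline and follow-up values to missing when reports conflict over time. Such a woman leaves the sample for that outcome, but may stay in the samples for the others, where her baseline value on that measure could be filled for the balance table.

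**The case against.** The strongest reply is that the plan already contains the right analysis. Footnote 35, and sensitivity analysis 2 in section 4f.iv, commit to unfilled estimates next to the benchmark. Missing-data prevalence by arm is also promised (section 4c.v step 2, footnotes 19 and 28). This stands. A reader might infer that the published balance will be distorted, but that goes too far, since the undistorted column will be published too. What remains is which column is called the benchmark.

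The size is also fairly disputed. The larger figures need a zero fill, which the SAP does not state, and unequal missingness in a questionnaire completed before the video by participants who are not shown their assignment. With 1,416 analysed (80% of 1,770, an assumption), a 3% v 8% split is about 4.1 standard errors, so chance would hardly produce it. Differential loss to follow-up or the over-time recoding could contribute, but no figure in the SAP supports that size.

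Two stronger readings are tempting and lack support. One is that the footnote 15 decision rests on filled figures: that footnote names neither a threshold nor a set of estimates, so this is only a plausible default. The other is that the dual-methods measure is hit hardest, because it is undefined for women without vaginal sex at baseline. Those women enter only under the Table 1 sample. Section 4a restricts the analysis to women with vaginal sex at both time points, and the opening paragraph of Balance Assessment Methods admits only participants with baseline data on the outcome. Either rule keeps them out.

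The absence of a flag from the balance equation is weak evidence by itself, since the impact-model equation lists none either. The point does not depend on it, because a flag would not fully repair a filled dependent variable.

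**Conclusion.** The point holds as one of method and labelling. Read literally, footnote 35 makes the benchmark balance statistics a mixture of answers and constants, and ranks the valid observed-value estimates as a sensitivity analysis. How much this matters cannot be known from the SAP. With low, equal missingness and mean fill it is minor (g × 0.97 at 5%, × 0.89 at 20%). Only unequal missingness combined with a constant far from the mean makes it material, and then in either direction (g of 0.053 or 0.135 for a true 0.100 in the examples). These sizes rest on assumed means, rates and constants.

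The SAP also contradicts itself on who is filled. The Balance Assessment Methods rule drops participants without baseline data on the outcome, whereas step 5 and footnote 18 keep and adjust them. If the first rule governs, each outcome's own baseline measure is never filled in its own sample, though other questionnaire items still can be. The documents do not show that the trial's balance will be misreported or a secondary outcome wrongly demoted.

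**What to change.** - In footnote 35, make the observed-value estimates, within each analytic sample, the benchmark for balance. State that step 5 is not applied to a variable when it is the dependent variable of the balance model.
- Keep dummy-variable adjustment for covariates in the impact models, and state the fill constant.
- Show the already planned missing counts by arm beside each balance variable.
- State in footnotes 15 and 16 that the demotion decision uses the observed-value estimates.
- Reconcile the sample rule in Balance Assessment Methods with step 5 and footnote 18, and the dual-methods sample in section 4a with Table 1.

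The cost is SAP wording only. Both balance runs are already planned, so they swap places and no new data or analysis is needed.
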